**Optional Lenvatinib Crossover (for Subjects in Arm B Only):**

Subjects in Arm B with disease progression per RECIST 1.1 may be eligible for optional treatment with lenvatinib±chemotherapy. Please see [Section 9.1.4](#) for further details.

**Duration of Treatment**

A subject will remain on study treatment until 1 or more of the following events occur(s):

- Progressive disease (as confirmed by IIR\*)
- Unacceptable toxicity
- Subject request
- Withdrawal of consent
- Termination of the study by the Sponsor

\*Confirmation of disease progression by IIR is only required during the Randomization Phase.

**Concomitant Drug/Therapy**

Prohibited Concomitant Therapies and Drugs

Subjects should not receive other antitumor therapies while on study. If a subject receives additional antitumor therapies other than the study drug(s), such as chemotherapy, targeted therapies, immunotherapy, or antitumor interventions - such as surgery or palliative radiotherapy (other than as described below), this will be judged to represent evidence of disease progression, and the study medication should be discontinued.

Bisphosphonates and denosumab for the treatment of osteosarcoma are not permitted.

The concomitant use of live vaccines (e.g., measles, mumps, rubella, chicken pox, yellow fever, rabies, BCG, and typhoid [oral] vaccines) are not permitted. Seasonal influenza vaccines for

injection are generally killed virus vaccines and therefore, are permitted. However intranasal influenza vaccines (e.g., FluMist®) are live attenuated vaccines, and therefore, are not permitted. Additionally, the concomitant use of live vaccines with chemotherapy is contraindicated in immunosuppressed patients.

For further information on the prohibited concomitant therapies for ifosfamide and etoposide, please refer to the respective prescribing information.

The following concomitant treatments/procedures are allowed:

- a. Removal of existing (not new) osteosarcoma lesion (eg, surgical, radiofrequency ablation, cryotherapy, thermoablation, stereotactic radiotherapy, etc.) after completion of the Week 18 tumor assessment. Subjects may continue study treatment after protocol permissible surgery, in the presence of clinical benefit, with Sponsor approval.
- b. Palliative radiotherapy is allowed for  $\leq 2$  significantly symptomatic nontarget lesions.

If a subject receiving treatment with lenvatinib requires surgery during the study, the stop time and restart time of lenvatinib should be as follows:

- For minor procedures: stop lenvatinib at least 2 days before the procedure and restart it at least 2 days after, once there is evidence of adequate healing and no risk of bleeding.
- For major procedures: stop lenvatinib at least 1 week (5 half-lives) prior to surgery and then restart it at least 2 weeks after, once there is evidence of adequate healing and no risk of bleeding.

Any additional procedural or subject specific particularities should be discussed with the sponsor.

## Assessments

### Efficacy Assessments

Tumor assessment will be performed based on RECIST 1.1. Investigator-determined response assessments will be performed at each assessment time point and entered onto the case report form (CRF). Copies of all tumor assessment scans will be sent to an imaging core laboratory (ICL) designated by the sponsor for efficacy assessment and for confirmation of PD. Tumor assessments will be carried out following the guidelines provided by the ICL.

During the Screening Period, tumor assessments of the chest, abdomen, pelvis, and other areas of known disease or newly suspected disease should be performed within 28 days prior to Cycle 1 Day 1. A brain scan (CT scan with contrast or MRI pre- and post-gadolinium) will be performed at screening as clinically indicated, and thereafter during the study as clinically indicated. Historical CT or MRI scans performed within 28 days prior to Cycle 1 Day 1 may be used as screening scans (baseline scans) to demonstrate eligibility, as long as they meet minimum standards as separately defined by the ICL.

If available, bone imaging obtained within 8 weeks prior to Cycle 1 Day 1 should be sent to the ICL. Bone lesions noted on the screening/baseline images should be followed as non-target lesions with modalities other than nuclear medicine scans.

Tumor assessments will then be performed every 6 weeks  $\pm 1$  week following the date of randomization until Week 18. Following completion of the chemotherapy treatment period (ie, after Week 18), the frequency of tumor assessments will be every 9 weeks  $\pm 1$  week until Week 54  $\pm 1$  week. Thereafter, they will be performed every 12 weeks  $\pm 2$  weeks until documentation of PD (please see [schedule of assessments](#) for details). At any point, the CT/MRI scan should be performed earlier than the scheduled time point, if clinically indicated. After data cutoff for the primary analysis, tumor assessments should be performed following the prevailing local standard of care.

Disease progression per RECIST 1.1 during the randomization phase must be confirmed by IIR prior to the investigator discontinuing study treatment.

In the event that the investigator considers alternative treatments must be instituted immediately for management of urgent medical complications of PD, study drugs may be discontinued without waiting for independent confirmation of radiographic evidence of PD. Subjects who discontinue study treatment without PD will continue to undergo tumor assessments according to the schedule until PD is documented or another anticancer therapy is initiated.

Prior to optional lenvatinib crossover, baseline tumor assessment must be re-established (i.e., new tumor assessment scans performed), unless the last tumor assessment scans were performed within 4 weeks prior to Cycle 1 Day 1 of the crossover treatment.

During the Optional Lenvatinib Crossover Treatment Phase, tumor assessments will be performed as clinically indicated per the institutional guidelines (but no less frequently than every 12 weeks), following the prevailing local standard of care. Scans are not required to be submitted to the independent imaging core laboratory during the Optional Lenvatinib Crossover Treatment Phase.

### **Pharmacokinetic Assessments**

Blood samples for plasma concentrations of lenvatinib will be collected from all subjects from Arm A only as described in the Schedule of Assessments. Pharmacokinetic sampling should not be performed for any subject with a body weight <13 kg (please see [Section 9.5.1.3.1](#)).

### **Pharmacodynamic and Other Biomarker Assessments**

Optional pharmacodynamic serum and archived fixed tumor tissue samples for biomarker analysis may be collected from subjects randomized to Arm A only, as described in the Schedule of Assessments. Pharmacodynamic sampling should not be performed for any subject with a body weight <16 kg (please see [Section 9.5.1.3.2](#) ). Pharmacodynamic serum and tumor biomarkers assessed in this study will be based on those identified in other lenvatinib clinical studies.

Pharmacodynamic biomarker analysis will be performed as described in a separate analysis plan.

Note: Providing blood samples for pharmacodynamic biomarker assessment is optional and will not impact subject eligibility.

### **Safety Assessments**

Safety assessments will consist of monitoring and recording all adverse events (AEs), including all grades per National Cancer Institute (NCI) CTCAE v5.0 (for both increasing and decreasing severity), and serious adverse events (SAEs); regular laboratory evaluation for hematology, blood chemistry, and urine values; periodic measurement of vital signs and ECGs; and physical examinations.

Progression of osteosarcoma and signs and symptoms clearly related to the progression of the osteosarcoma should not be captured as an AE. Disease progression is a study endpoint and should be captured in the CRF as per the guidelines for reporting disease progression.

### **Other Assessments**

HRQoL assessment will be performed per the Schedule of Assessments. Impact of treatment on HRQoL will be assessed using the PedsQL (including the Generic Core Scales and Cancer Module).

### **Bioanalytical Methods**

Lenvatinib in plasma will be quantified using a validated liquid chromatography tandem mass spectrometry (LC-MS/MS) method. Pharmacodynamic biomarker analysis will be performed as described in a separate analysis plan. Clinical laboratory tests will be performed at qualified local laboratories.

## Statistical Methods

### Study Endpoints

Efficacy endpoints related to tumor assessments will be evaluated by independent imaging review (IIR) and investigator assessment.

#### Primary Endpoint

**PFS (progression-free survival) by IIR** is defined as the time from the date of randomization to the date of the first documentation of PD or death (whichever occurs first) as determined by IIR using RECIST 1.1.

#### Secondary Endpoints

- **PFS-4m rate (progression-free survival rate at 4 months) by IIR** is defined as the percentage of subjects who are alive and without PD at 4 months from the randomization date as determined by IIR of radiological imaging using RECIST 1.1. The PFS-4m rate is estimated using the Kaplan-Meier (K-M) method.
- **PFS-1y rate (progression-free survival rate at 1 year) by IIR** is defined as the percentage of subjects who are alive and without PD at 1 year from the randomization date as determined by IIR of radiological imaging using RECIST 1.1. The PFS-1y rate is estimated using the K-M method.
- **Overall survival (OS)** is defined as the time from the date of randomization to the date of death from any cause. Subjects who are lost to follow-up and those who are alive at the date of data cutoff for the primary analysis, will be censored at the date the subject was last known to be alive, or date of data cutoff for the primary analysis, whichever occurs first. Overall survival rate at 1 year (OS-1y) will be estimated using the K-M method.
- **Objective response rate by IIR at 4 months (ORR-4m)** is defined as the proportion of subjects who have best overall response of complete response (CR) or partial response (PR) as determined by IIR using RECIST 1.1 within the first 4 months.
- **Objective response rate (ORR) by IIR** is defined as the proportion of subjects who have best overall response of complete response (CR) or partial response (PR) as determined by IIR using RECIST 1.1.
- **Safety** will be assessed summarizing the incidence of treatment-emergent adverse events (TEAEs) and SAEs together with all other safety parameters.
- Assessment of population-based PK parameters of lenvatinib.
- Score changes from baseline for all PedsQL scales including Generic Core Scales and Cancer Module. Scores will be calculated for total generic score, total cancer score, each physical function subscale including physical health, psychosocial health, emotional function, social function, school/work function in the Generic Core Scales, and each subscales in the cancer module.
- Palatability and acceptability of the suspension formulation of lenvatinib in subjects receiving the suspension formulation in the study will be assessed using the Palatability Questionnaire (see [Appendix 4](#)).

#### Exploratory Endpoints

- **Duration of response (DOR) by IIR and investigator assessment** is defined as the time from the date a response was first documented until the date of the first documentation of PD or date of death from any cause.
- **Disease control rate (DCR) by IIR and investigator assessment** is the proportion of subjects who have a best overall response of CR or PR or stable disease (SD). In this context, stable

disease is defined as stable disease at  $\geq 7$  weeks after randomization to be considered best overall response.

- **Clinical benefit rate (CBR) by IIR and investigator assessment** is the proportion of subjects who have best overall response of CR or PR or durable SD (duration of SD  $\geq 23$  weeks after randomization).
- Efficacy endpoints (PFS, PFS-4m, PFS-1y, ORR-4m, and ORR) evaluated based on investigator assessment
- Proportion of subjects who achieve complete removal of baseline lesions.
- **Blood and tumor biomarkers** will be assessed for identifying potential correlation with clinical outcomes-related endpoints.

#### Analysis Sets

**The Full Analysis Set (Intent-to-Treat Analysis [ITT])** includes all randomized subjects regardless of the treatment actually received. This is the primary analysis population used for the efficacy analyses which will be based on the ITT principle.

**The Per Protocol Analysis Set** includes those subjects from the ITT set who received at least 1 dose of any study drug, had no major protocol deviations and had both baseline and at least one postbaseline tumor assessment. Subjects for whom death occurred prior to the first postbaseline tumor assessment will also be included. The per protocol analysis set will be the secondary analysis set for efficacy endpoints.

**The Safety Analysis Set** includes subjects who received at least 1 dose of any study drug. This is the analysis population used for all safety analyses which will be based on as-treated principle.

**Population Pharmacokinetic (PK) Analysis Set** includes the subjects who have received at least 1 dose of lenvatinib with documented dosing history and have measurable plasma levels of lenvatinib.

**The Pharmacodynamic Analysis Set** includes subjects who received at least 1 dose of study drug and had sufficient pharmacodynamic data (eg, at least 1 evaluable/measurable pharmacodynamic parameter).

**The HRQoL Analysis Set** will consist of all randomized subjects who have received at least 1 dose of study medication, and have at least 1 patient-reported outcome (PRO) assessment completed beyond baseline. For PRO analysis, subjects will be analyzed as randomized and not according to treatment actually received.

#### Efficacy Analyses

Efficacy analyses will be based primarily on the Full Analysis Set.

All primary statistical analyses will be conducted at the data cutoff date for the primary analysis (ie, when approximately 38 PFS events, as determined by IIR, are observed).

#### Primary Analysis

Progression-free survival (PFS) will be analyzed and compared between the 2 treatment arms using the stratified log-rank test with time to first relapse/refractory disease (early [ $<18$  months] or late [ $\geq 18$  months]) and age ( $<18$  or  $\geq 18$  years) as strata. PFS censoring rules will follow FDA guidance of 2007 and will be detailed in the statistical analysis plan. Median PFS will be calculated using the Kaplan-Meier (K-M) product-limit estimates for each treatment arm along with 2-sided 95% confidence intervals (CIs). The K-M estimates of PFS will be plotted over time. The Cox regression model will be used to estimate the hazard ratio and its 95% CIs stratified by the stratification factors.

### **Secondary Analyses**

The PFS-4m rate and PFS-1y rate will be estimated on the Full Analysis Set using the K-M method for the primary efficacy PFS analysis. PFS-4m/PFS-1y rate and their Greenwood standard errors will be evaluated using the K-M estimates from both treatment groups. The statistical significance of the difference in the 2 K-M PFS-4m rates will be based on its 2-sided 95% CI. This 2-sided 95% CI and a p-value will be constructed using the difference of these 2 K-M PFS-4m/PFS-1y rates and the 2 corresponding Greenwood standard errors.

Overall survival (OS) will be compared between treatment arm and control arm following the same statistical method for the primary efficacy PFS endpoint. Kaplan-Meier (K-M) estimates of OS rate will also be presented for 4, 6, 9, and 12 months with 2-sided 95% CIs.

The ORR will be summarized and compared between the two treatment arms using stratified Miettinen and Nurminen's method. The difference in ORR and its 2-sided 95% confidence interval from the stratified Miettinen and Nurminen's method with strata weighting by sample size will be reported. The stratification factors used for randomization will be applied to the analysis. The ORR-4m will be summarized and compared between arms using the same approach as for ORR.

### **Exploratory Analyses**

Median DOR among responders for each arm will be presented along with its corresponding 2-sided 95% CIs. Disease Control Rate (DCR) and CBR will be summarized and compared between arms using the same approach as for ORR.

### **Pharmacodynamic and Other Biomarker Analyses**

Pharmacodynamic, and other biomarker analyses may be performed and reported separately. Details of these analyses may be described in a separate analysis plan.

Blood serum samples may be analyzed using global proteomic methods, enzyme-linked immunosorbent assay (ELISA), multiplex bead-based immunoassay, or other assays/methods and new technology in an effort to identify biomarkers.

Archived, fixed tumor tissue will be collected (if available) for assessment of mutations and other genetic alterations or proteins that may be important in the development and progression of cancer as well as for potential use in diagnostic development.

Data obtained from the pharmacodynamic samples will be used for research. The pharmacodynamic samples will not be used to determine or predict risks for diseases that an individual subject does not currently have. Any sample or derivatives (DNA, RNA, and protein) may be stored for up to 15 years to assist in any research scientific questions related to lenvatinib and for potential diagnostic development. If the subject reaches the age of 18 years (or at the appropriate age per local country requirements) while on the study, and becomes competent to give informed consent, his/her consent will be obtained using separate informed consent forms (ICFs) to continue on the study. Further analyses will not be performed on samples collected from subjects who do not reconsent at the age of 18 years (or at the appropriate age per local country requirements).

### **Pharmacokinetic Analyses**

Lenvatinib concentration versus time data will be tabulated and summarized and graphically presented.

Lenvatinib data from Arm A of the study will be pooled with available data from other studies and subjected to population PK analysis. The PK model will be parameterized in terms of clearance

and volume of distribution. Details of the population PK analysis will be provided in a separate analysis plan.

#### **Other Analyses**

Health-Related Quality of Life (HRQoL):

The PedsQL for all subjects(self- and proxy-rating) will be collected at baseline, at C2D1, C3D1, Week 18, C8D1, C18 D1, and at the Off-Treatment visit.

#### **Interim Analyses**

No interim analysis is planned for this study.

The safety monitoring will be conducted by the independent data monitoring committee (IDMC). The frequency of safety reviews will be defined in the IDMC charter. Minutes from the open meetings of the IDMC will be provided if requested by regulatory agencies. The recommendation whether to stop the study for safety will be reached by the IDMC based on their review of safety data with treatment information. The function and membership of the IDMC will be described in the IDMC charter.

#### **Sample Size Rationale**

A total sample size of 72 subjects is estimated for the primary efficacy endpoint of PFS. Assuming a hazard ratio of 0.4 (median PFS of 3.5 and 8.75 months for the control arm and the test arm, respectively), a one-sided type 1 error rate of 0.025, and power of 80%, 38 PFS events are required for the primary analysis. The total sample size of 72 subjects is estimated to achieve 38 PFS events assuming the analysis occurs approximately 32 months after the first subject is randomized (assuming a 20-month enrollment period), and accounts for a dropout rate of up to 40%.

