### Study Design

E7080-G000-230 is a multicenter, randomized, open-label, parallel-group, Phase 2 study to compare the efficacy and safety of lenvatinib in combination with ifosfamide and etoposide versus ifosfamide and etoposide in children, adolescents, and young adults with relapsed or refractory osteosarcoma.

Approximately 72 eligible subjects will be randomized to 1 of the following 2 treatment arms in a 1:1 ratio within the strata:

- Arm A: lenvatinib 14 mg/m^2 (orally, once daily) plus ifosfamide 3000 mg/m^2/day (intravenously [IV], Day 1 to Day 3 of each cycle for a total of up to 5 cycles) and etoposide 100 mg/m^2/day (IV, Day 1 to Day 3 of each cycle for a total of up to 5 cycles)
- Arm B: ifosfamide 3000 mg/m^2/day (IV, Day 1 to Day 3 of each cycle for a total of up to 5 cycles) and etoposide 100 mg/m^2/day (IV, Day 1 to Day 3 of each cycle for a total of up to 5 cycles)

Randomization will follow a predefined randomization scheme based on the following stratification factors: time to first relapse/refractory disease (early [<18 months] or late [>18 months]) and age (<18 and ≥18 years).

The Sponsor will closely monitor enrollment, to ensure that a minimum of 36 subjects are <17 years of age at the time of informed consent.

The study will be conducted in 3 Phases: a Prerandomization Phase, a Randomization Phase, and an Extension Phase.

The **Prerandomization Phase** will consist of 2 periods: Screening and Baseline. The Prerandomization Phase will last no longer than 28 days. The Screening Period will establish protocol eligibility and the Baseline Period will confirm eligibility.

The **Randomization Phase** will consist of 2 periods: Treatment Period and Follow-up Period. The Randomization Phase will begin at the time of randomization of the first subject and will end on the data cutoff date for the primary analysis (ie, when approximately 38 PFS events, as determined by IIR, are observed). After the data cutoff date for the primary analysis has occurred, all subjects who are still on study treatment will enter the Extension Phase.

The **Treatment Period** for each subject will begin at the time of randomization and will end at the completion of the Off-Treatment Visit, which will occur within 30 days after the final dose of study treatment.

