#### 9.7.1.6.1 PRIMARY EFFICACY ANALYSIS

The primary efficacy endpoint of progression-free survival (PFS) per IIR will be analyzed and compared between the 2 treatment arms using the stratified log-rank test with time to first relapse/refractory disease (early [ $<18$  months] or late [ $\geq 18$  months]) and age ( $<18$  or  $\geq 18$  years) as strata. PFS censoring rules will follow FDA guidance of 2007 and will be detailed in the statistical analysis plan. Median PFS will be calculated using the K-M product-limit estimates for each treatment arm along with 2-sided 95% CIs (estimated with a generalized Brookmeyer and Crowley method [Brookmeyer and Crowley (1982)]). The K-M estimates of PFS will be plotted over time. The Cox regression model will be used to estimate the hazard ratio and its 95% CIs stratified by the stratification factors.

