#### 9.7.2 Determination of Sample Size

A total sample size of 72 subjects is estimated for the primary efficacy endpoint of PFS. A median PFS of 3.5 months for Arm B (control arm) has been estimated by comparing available PFS data from clinically active agents in this patient population ([Davis, et al., 2019](#); [Palmerini, et al, 2016](#); [Grignani, et al., 2012](#)). With respect to Arm A (lenvatinib plus chemotherapy arm), a median PFS of 8.75 months is estimated based on the results from Study 207.

Therefore, assuming a hazard ratio of 0.4, a 1-sided type 1 error rate of 0.025, and power of 80%, the required number of PFS events for the study is 38. The primary PFS analysis is estimated to occur at approximately 32 months after the first subject is randomized (assuming a 20-month enrollment period), and accounts for a dropout rate of up to 40%.

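### At 38 events the stratified log-rank test named as the primary analysis has roughly 73–75% power, not the stated 80%

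*Protocol*

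**What the plan says.** The synopsis, under Sample Size Rationale, sets out the design: "Assuming a hazard ratio of 0.4 (median PFS of 3.5 and 8.75 months for the control arm and the test arm, respectively"), with "a one-sided type 1 error rate of 0.025, and power of 80%, 38 PFS events are required for the primary analysis". Section 9.7.2 repeats the count: "the required number of PFS events for the study is 38".

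On size and timing the synopsis says "A total sample size of 72 subjects is estimated for the primary efficacy endpoint of PFS", "assuming the analysis occurs approximately 32 months after the first subject is randomized (assuming a 20-month enrollment period"), and that the plan "accounts for a dropout rate of up to 40" per cent. It does not say when dropout occurs, names no sample-size formula and mentions no allowance for stratification.

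The primary analysis in Section 9.7.1.6.1 is "compared between the 2 treatment arms using the stratified log-rank test". The strata are time to first relapse or refractory disease (under 18 months, or 18 months and over) and age (under 18, or 18 and over). Randomisation assigns subjects to "treatment arms in a 1:1 ratio within the strata". The data cutoff is event-driven, at about 38 PFS events by independent review (synopsis, Efficacy Analyses; Section 9.7.1.6).

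**The concern.** The event count and the test do not match. Schoenfeld's formula, which reproduces 38, treats the log-rank test as unstratified and is a local approximation that works best when the effect is small. Here the effect is large (hazard ratio 0.4), and the test splits 38 events over four strata. Both features reduce the power actually obtained.

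This is the trial's one primary comparison and no interim analysis is planned. If the stated 80% is too high, a non-significant result will be set against a 20% chance of missing a true hazard ratio of 0.4 when that chance is nearer 25–27%.

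**Working it through.** **Inputs from the protocol:** hazard ratio 0.4; medians 3.5 and 8.75 months; one-sided 0.025; 72 subjects, 1:1; 20-month enrolment; cutoff at the 38th event; log-rank test on 2 × 2 strata.

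**Assumptions, not in the protocol:** exponential PFS; uniform accrual; permuted blocks of 4 within strata; stratum shares of 50/50, 60/35, 75/50 and 80/70 for the two factors.

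**Step 1. Reproduce the plan's figures.**

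- Schoenfeld events: 4 × (1.96 + 0.8416)² / (ln 0.4)² = 37.4, rounded up to 38.
- Power at 38: √38/2 × 0.916 − 1.96 = 0.864, which corresponds to 80.6%.
- The probability of an event by month 32 is 0.977 (control) and 0.806 (test), mean 0.892. Then 38/0.892 = 42.6, rounded up to 43, and 43/(1 − 0.40) = 71.7, rounded up to 72.

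So 38 events, 72 subjects and month 32 all reproduce. The last two do so when 40% of subjects are treated as giving no event.

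**Step 2. Check the approximation at this hazard ratio.** Freedman's formula gives (1.96 + 0.8416)² × (1.4/0.6)² = 42.7 events for 80% power. At 38 events, √38 × 0.6/1.4 − 1.96 = 0.682, or 75.2%. The two standard formulas differ by five points, so simulation is needed.

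**Step 3. Simulate the named test.** There were 10,000 trials per scenario, so the Monte Carlo standard error is about √(0.74 × 0.26/10,000) = 0.4 points.

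| Scenario, 38 events unless stated | Unstratified | Stratified |
|---|---|---|
| No dropout, shares 50/50 (two seeds) | 77.9–78.2% | 73.6–73.9% |
| No dropout, 60/35 | 78.6% | 74.6% |
| No dropout, 75/50 | 77.9% | 74.0% |
| No dropout, 80/70 | 78.6% | 75.1% |
| One factor doubles the hazard | 73.5% | 72.8% |
| Exponential dropout, 40% by 12 months | 78.5% | 73.8% |
| 40% drop out uniformly over 12 months | 77.5% | 73.6% |
| 40% drop out uniformly over 6 months | 77.8% | 73.4% |
| 40% of subjects give no event | 76.8% | 69.8% |
| No treatment effect (type I error) | 2.4% | 2.6% |
| 43 events, no dropout | 83.0% | 79.7% |
| 44 events, no dropout | 84.1% | 80.9% |

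Separately coded runs agree to within about two points: 74–76% without dropout and 70–71% on the no-event reading. The most favourable settings tried were instant accrual (78%) and progression dated at scan visits (77%). No scenario at 38 events reached 80%.

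**Step 4. Test the 44-event alternative.** With 40% annual exponential dropout, 44 events give 80.6% power, are reached in over 99% of trials and arrive at about month 22–23. If 40% of subjects give no event, only 72 × 0.6 = 43.2 subjects on average can have one. Then 52% of simulated trials never reach 44 events, and power is 73%.

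**The case against.** The strongest reply is that nothing has been miscalculated. Using the unstratified event formula for a stratified log-rank test is a common planning convention, and the protocol does not claim that the figure is exact for the stratified statistic. That stands in part: a reader might infer an arithmetic error, and there is none. The unstratified test at 38 events has about 78% power, within normal approximation error of 80%. But the power statement describes this trial's primary analysis, and the further four to five points lost on stratifying go beyond that tolerance.

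A reader might also infer that power is 70% on the protocol's own dropout assumption. The text does not support that. It gives a ceiling with no time pattern, and dropout spread over time leaves power at 73–74%. The no-event reading does matter, because of the dropout patterns tried it is the one that reproduces both 72 subjects and roughly month 32. It therefore belongs beside the main figure as a condition.

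The result also depends on unstated quantities: stratum shares, prognostic strength and block size. Stratum shares barely move it. Prognostic strength moves it more: one run of 4,000 trials with both factors doubling the hazard gave 71%. A range is the right form of statement.

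Finally, the assumed effect is much less certain than five points of power. Study 207 reported a median PFS of 11.1 months (95% CI 4.5 to 12.6). At 11.1 against 3.5 months the hazard ratio is 0.315 and stratified power at 38 events is about 90%; at the lower limit it would be far less. That limits the practical consequence, but it does not make 80% correct under the assumptions the protocol states.

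**Conclusion.** The concern holds as a moderate overstatement of power. Under the stated hazard ratio, medians, accrual and 38-event cutoff, the stratified log-rank test has roughly 73–75% power. That rests on exponential PFS, assumed stratum shares and block size, and dropout that is absent or spread over time. If 40% of subjects contribute no event, power is about 70%, and 8–9% of trials never reach 38 events.

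Two further inferences should be resisted. First, type I error is sound: the simulated one-sided level is 2.6%. Second, the month-32 date does not rescue the power. Without dropout, 72 × 0.892 = 64 events would accrue by then, but the cutoff is set by events, and the 38th arrives at about month 18, before enrolment ends.

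Nor does the finding argue against stratifying. When one factor is prognostic, the unstratified test loses nearly as much (73.5% against 72.8%).

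**What to change.** In the synopsis (Sample Size Rationale) and Section 9.7.2:

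- Say that 38 events come from the unstratified approximation, if the sponsor confirms this.
- Restate the power of the stratified log-rank test at 38 events as roughly 73–75%, or about 70% if 40% of subjects contribute no event.
- State the dropout pattern assumed.

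This costs a few sentences and no patients, and it holds whatever the dropout pattern.

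If 80% is wanted, a trigger of about 44 events gives it within 72 subjects when dropout is low or spread over time, about three months later than the 38th event under 40% annual dropout. It should be adopted only after the dropout pattern is fixed: on the no-event reading about half of trials would never reach it, so it is an option and not a replacement for restating the power.
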